8.3.2 Sample Size Derivation

Sample size was determined by estimating the number of potential patients likely to be (approximately 50% of referred patients meeting the eligibility criteria) to the UTSW Department of Radiation Oncology over a three year period. We estimate that approximately 50-60 patients meeting entry criteria will present to our facility over the accrual period of 3 years. Of these patients, slightly more than 50%, or 25-30 patients, will consent to be evaluated for the protocol. Of these patients, approximately 80% will meet the Image Guided Hypofractionated Radiation Treatment constraints for total of 20-24 patients enrolled over 3 years. Twenty one patients are required for a 80% power of detecting the improved pelvic local control for 2 year follow-up. The sample size was estimated using the SWOG one-sample survival calculator: http://www.swogstat.org/stat/public/one_survival.htm

8.4 Patient Accrual and Study

8.4.1 Duration

It is expected that it will take approximately three years to meet the accrual goal. The analysis for acute toxicity will be carried out after each patient has had at least 90 days of follow-up from the end of the radiation therapy. Study-related data will be stored for 5 years after

termination of the study when accrual is no longer taking place and all patients have discontinued follow-up procedures.

8.5.2 The Analysis of Severe Late GU/GI Toxicity

This analysis will be carried out when each patient has had at least 90 days (i.e., 3 months) of follow-up after the end of the acute period. The time to the occurrence of severe late GU/GI toxicity is defined as the time interval from start of protocol treatment to the date of onset of grade 3-5 GU/GI toxicity. A Kaplan-Meier curve will be used to estimate the time to late toxicity. The time analysis for recording severe late GU/GI toxicity for this protocol will be limited to 180 days from after completion of protocol therapy, although every effort will be made to document any late toxicity during subsequent follow-up. If no such toxicity is observed before the time of the analysis, the patient will be censored at the time of the analysis.

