2.2 Secondary Objectives

- 2.2.1 To determine the acute (< 90 days) and late (90-365 days) grade ≥ 3 GI and GU toxicity as assessed by CTCAEv4 from the commencement of Image Guided Hypofractionated Radiation Treatment boost.
- 2.2.2 To determine the patient reported quality of life (FACT-CX)

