8.2 Secondary Endpoints

The secondary objectives are to:

- Determine the late grade ≥ 3 GI and GU toxicity as assessed by CTCAE v4 at 91-365 days from the start of protocol treatment. *This will be summarized using a proportion and a 95% confidence interval.*
- Measure Cervix cancer specific patient reported QOL at 6 time points using FACT-CX validated measurement tools with our VTOC system

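### Section 8.5.2 defines time to severe late GU/GI toxicity with no lower time bound, so, applied as written, acute events enter the late-toxicity Kaplan-Meier curve and can hide later events on it

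*Combined protocol and SAP*

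**What the plan says.** Three sections deal with late toxicity, and each describes a different period.

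- **2.2.1** takes as a secondary objective "late (90-365 days) grade ≥ 3 GI and GU toxicity", counted from the start of the boost, with acute toxicity as anything before day 90.
- **8.2** places late toxicity "at 91-365 days from the start of protocol treatment" and summarizes it as a proportion with a 95% confidence interval.
- **8.5.2** calls its variable severe late GU/GI toxicity, and the time to it "is defined as the time interval from start of protocol treatment to the date of onset of grade 3-5 GU/GI toxicity". The estimator follows: "A Kaplan-Meier curve will be used to estimate the time to late toxicity". The only censoring rule is: "If no such toxicity is observed before the time of the analysis, the patient will be censored at the time of the analysis". The analysis is run once each woman has "at least 90 days (i.e., 3 months) of follow-up after the end of the acute period", and the period analyzed "will be limited to 180 days from after completion of protocol therapy".

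Section 8.5.1 adds proportions for acute and late toxicity among treated patients, with exact binomial intervals, and a general Kaplan-Meier curve for time to toxicity.

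**The concern.** The sentence that a programmer would code in 8.5.2 has an origin and an event but no lower time limit. The section mentions the end of the acute period only to time the analysis, not to restrict the event. It gives no landmark, no delayed entry and no rule for a woman who has already had an acute event.

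Two things follow if it is coded literally. A grade 3 diarrhea on day 30 becomes an event on the late curve. And because Kaplan-Meier uses one event time per woman, she then leaves the risk set, so a stricture or fistula on day 150 does not appear on that curve. Section 1.1 names stricture and fistula among the toxicities that it expects to be dose-limiting.

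At stake is whether the curve and the proportion, both reported as late toxicity, describe the same thing. With 21 women, one or two events assigned to the wrong period visibly change the result.

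**Working it through.** **The plan's own figure.** No number is stated for the late curve. The figure that fixes its denominator is N = 21 (8.3.1), and it reproduces. With exponential survival, λ0 = −ln(0.65)/2 = 0.2154 and λ1 = −ln(0.85)/2 = 0.0813. With 2 years of accrual and 2 of follow-up, the event probability under the alternative is p1 = 0.215, and w0 = p1 × λ0/λ1 = 0.571. The one-sample log-rank formula gives n = [1.645√0.571 + 0.842√0.215]² / (0.571 − 0.215)² = 21.1. Nothing below changes it.

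**The definitions side by side.**

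| | 2.2.1 | 8.2 | 8.5.2 |
|---|---|---|---|
| Origin | start of boost | start of protocol treatment | start of protocol treatment |
| First day counted | 90 | 91 | none stated |
| Last day counted | 365 | 365 | 180 days after completion |
| Summary | none stated | proportion | Kaplan-Meier |

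Section 1.1 has the boost delivered over 2-3 weeks. The 8.5.2 limit therefore falls at about day 14 + 180 = 194 to 21 + 180 = 201 from boost start, well short of day 365. The earliest analysis time is 90 + 90 = 180 days from the start of the acute period. An onset on day 90 is late under 2.2.1 but not under 8.2. If protocol treatment is taken to begin with pelvic radiation, toxicity from that phase would enter the 8.5.2 curve as well.

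**Size, by illustration.** Inputs:

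- Acute rate a: 9-19%. Section 8.3.1 cites prior grade ≥3 rates of 7-14% (GI) and 2-5% (GU). Adding them assumes no overlap, and treating them as acute is an assumption because no time window is given.
- Late rate l: 5-10%. This is an assumption; the documents give none.
- Acute and late events independent, no censoring.

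As written, the curve ends at 1 − (1 − a)(1 − l). With onset restricted to the late period it ends at l. The acute share of events is a divided by the curve value. The expected number of women whose late event is hidden is 21 × a × l.

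| a | l | Curve as written | Ratio to l | Acute share | Women hidden |
|---|---|---|---|---|---|
| 9% | 5% | 13.6% | 2.7 | 66% | 0.09 |
| 9% | 10% | 18.1% | 1.8 | 50% | 0.19 |
| 19% | 5% | 23.1% | 4.6 | 82% | 0.20 |
| 19% | 10% | 27.1% | 2.7 | 70% | 0.40 |

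Independence matters for the last column: if late events occurred only in women with an earlier acute event, every late event would be hidden.

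**A concrete case.** Of 21 women, suppose 3 have an acute event, 2 have a late event, and 1 of these has both. As written, the curve has 3 + 2 − 1 = 4 events: 4/21 = 19.0% (exact 95% CI 5.4-41.9%). Three of the four are acute, and one of the two late events is not shown. With onset restricted to the late period it has 2/21 = 9.5% (CI 1.2-30.4%).

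**Censoring.** Read literally, a woman who dies or leaves without an event stays in the risk set until the analysis date. That counts time in which no event could be observed and pulls the curve down, in the opposite direction to the missing lower bound.

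**The case against.** The best defense is that late is already a defined term. Section 8.5.2 uses it in its heading, in the clause that names the variable and in the Kaplan-Meier sentence, and the censoring rule refers back to such toxicity. The defining sentence may be meant only to fix origin and endpoint for an event already understood to be late. Section 8.5.1 also plans a general time-to-toxicity curve, which the literal reading would largely duplicate for GI/GU events. This is plausible, and it means that contamination of the curve is certain only if the definition is applied as written. It does not remove the problem. The two windows that could be imported have different origins and different first days, and the 180-day limit in 8.5.2 matches neither end. Two careful analysts could draw different curves from the same data.

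Stronger readings that a reader might infer are not supported:

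- *Late events are lost to the trial.* They are lost to this curve only; the proportions in 8.2 and 8.5.1 can still count them. Under independence the expected number hidden is below one woman.
- *The curve can never be compared with a late rate.* Onset times are the variable plotted, so events after the acute period can be separated from the same data.
- *Women gone before day 90 distort even a corrected curve, so a landmark is essential.* Once events are limited to the late period and women are censored at death or last contact, those who left earlier are in no later risk set. The estimate then equals the day-90 landmark estimate.
- *The primary conclusion or early stopping is compromised.* The primary test concerns local control, and the stopping rules in 10.3 do not refer to this curve.

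**Conclusion.** The point holds as a defect in a stated rule for a secondary, descriptive analysis, and it should be corrected. On its literal terms 8.5.2 estimates acute plus late GI/GU toxicity under a late label. Under the assumptions shown, the curve would read about 14-27% where the late rate is 5-10%, a factor of 1.8 to 4.6. The direction follows from the wording. The size is illustrative, since it rests on an assumed late rate, on treating the prior rates as acute, and on independence.

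A lower bound alone would not make the curve and the proportion agree, because the curve would still stop at 180 days after therapy while the proportion runs to day 365.

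**What to change.** Rewrite the definition in 8.5.2 as follows, and align 2.2.1 and 8.2 with it in the same edit:

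1. The event is the first grade 3-5 GI/GU toxicity with onset after the acute period, within the same late window as 2.2.1 and 8.2.
2. An earlier acute event does not end a woman's risk of a late one.
3. Event-free women are censored at death or last contact, not at the date of the analysis.
4. One time origin (boost start or start of protocol treatment, with the latter defined if it is used), one first day (90 or 91) and one upper limit (180 days after completion or day 365) apply to both the curve and the proportion. The analysis is timed so that the chosen window can be observed.

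The cost is wording. The definition already depends on onset dates, so the lower bound needs no new data item, and the sample size and the primary analysis do not change.

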8.6 Gender and Diversity

Projected Ethnic Diversity

	Gender		
Ethnic Category	Females	Males	Total
Hispanic or Latino	10	NA	10
Not Hispanic or Latino	11	NA	11
Ethnic Category: Total of all	21	NA	21
	Gender		
Racial Category	Females	Males	Total
American Indian or Alaskan Native	0	NA	0
Asian	1	NA	1
Black or African American	6	NA	6
Native Hawaiian or other Pacific	0	NA	0
White	14	NA	14
Racial Category: Total of all	21	NA	21

NA = Not Applicable

9. STUDY MANAGEMENT

9.1 Conflict of Interest

Any investigator who has a conflict of interest with this study (patent ownership, royalties, or financial gain greater than the minimum allowable by their institution, etc.) must have the conflict reviewed by the University of Texas – Southwestern medical center IRB. All investigators will follow the University conflict of interest policy.

9.2 Institutional Review Board (IRB) Approval and Consent

It is expected that the IRB will have the proper representation and function in accordance with federally mandated regulations. The IRB should approve the consent form and protocol.

In obtaining and documenting informed consent, the investigator should comply with the applicable regulatory requirement(s), and should adhere to Good Clinical Practice (GCP) and to ethical principles that have their origin in the Declaration of Helsinki.

Before recruitment and enrollment onto this study, the patient will be given a full explanation of the study and will be given the opportunity to review the consent form. Each consent form must include all the relevant elements currently required by the FDA Regulations and local or state regulations. Once this essential information has been provided to the patient and the investigator is assured that the patient understands the implications of participating in the study, the patient will be asked to give consent to participate in the study by signing an IRB approved consent form.

Prior to a patient's participation in the trial, the written informed consent form should be signed and personally dated by the patient and by the person who conducted the informed consent discussion.

9.3 Required Documentation

Before the study can be initiated at any site, the following documentation must be provided to the research office.

- A copy of the official IRB approval letter for the protocol and informed consent
- IRB membership list
- CVs and medical licensure for the principal investigator and any associate investigators who will be involved in the study
- Form FDA 1572 appropriately filled out and signed with appropriate documentation (NOTE: this is required if institution holds the IND. Otherwise, the affiliate Investigator's signature on the protocol is sufficient to ensure compliance)
- A copy of the IRB approved consent form
- CAP and CLIA Laboratory certification numbers and institution lab normal values
- Executed clinical research contract

9.4 Registration Procedures

All patients must be registered with the Research Office before enrollment to study. Prior to registration, eligibility criteria must be confirmed with the Research Office Study Coordinator.

10. DATA & SAFETY MONITORING

10.1 Data Management and Monitoring/Auditing

10.1.1 External Data and Safety Monitoring Board

The UTSW Simmons Cancer Center (SCC) Data Safety Monitoring Committee (DSMC) is the external review of trial-related documentation, which may include detailed assessment of subject records, regulatory and pharmacy review or may be more focused depending on the nature and reason for the audit. External reflects an independent reviewer within the CRO who is external to the DOT. DSMC audits are performed by the Quality Assurance and Education Coordinator (QAC) with the overall purpose of reviewing the conduct of a clinical trial to ensure quality results. The audit schedule prioritizes investigator-initiated institutional therapeutic trials and frequency is determined by the risk of the trial.

The SCC DSMC meets quarterly and conducts annual comprehensive reviews of ongoing clinical trials, for which it serves as the DSMC of record. The Quality Assurance and Education Coordinator (QAC) works as part of the DSMC to conduct regular audits based on the level of risk. Audit findings are reviewed at the next available DSMC meeting. In this way, frequency of DSMC monitoring is dependent upon the level of risk. Risk level is determined by the DSMC Chairman and a number of factors such as the patient population to be studied; adequacy of the data management system; and procedures to ensure the safety of study subjects based on the associated risks of the study.

10.1.2 Internal Data and Safety Monitoring Committee

The Radiation Oncology Clinical Research Office (CRO) reports serious adverse events (SAEs) to Radiation Oncology Safety Assurance Committee (ROSAC) monthly. These SAEs are also reported to the University of Texas Southwestern Medical Center (UTSW) IRB per IRB guidelines and SCC DSMC.

All clinical trials are reviewed on monthly basis for enrollment. These trials are assessed for safety on a continual basis throughout the life of the trial. For investigator-initiated trials, all SAEs are monitored – both local and at affiliated institutions.

A data safety monitoring committee including radiation oncologists not participating in this trial will be formed to review toxicity endpoints and efficacy data. In the phase I component, the data safety monitoring committee will review and verify all reported DLTs. In particular, this committee will scrutinize the grading of adverse events and the attribution to therapy previously assigned by the investigators. This panel will have access to basic patient information so as to have the ability to critically review toxicity events. This study will use this committee to perform ongoing safety assessment at regular defined intervals defined in the statistics section of this protocol. Unexpected toxicities occurring between defined interim analyses points will be reported to the treating center's IRB and also to the University of Texas Southwestern Institutional Review Board.

Trial monitoring will be conducted no less than annually and refers to a regular interval review of trial related activity and documentation performed by the DOT, which includes but is not limited to accuracy of case report forms, protocol compliance, timeliness and accuracy of Velos entries and AE/SAE management and reporting. Documentation of trial monitoring will be maintained along with other protocol related documents and will be reviewed during internal audit.

10.2 Adverse Events: Definitions and Reporting

Adverse Events will be reported as indicated by the appropriate following table (see below).

10.2.1 Definition

An adverse event is defined as any untoward or unfavorable medical occurrence in a human research study participant, including any abnormal sign (for example, abnormal physical exam or laboratory finding), symptom, clinical event, or disease, temporarily associated with the subject's participation in the research, whether or not it is considered related to the subject's participation in the research.

Adverse events encompass clinical, physical and psychological harms. Adverse events occur most commonly in the context of biomedical research, although on occasion, they can occur in the context of social and behavioral research. Adverse events may be expected or unexpected.

10.2.2 Severity

Adverse events will be graded by a numerical score according to the NCI Common Terminology Criteria for Adverse Events (NCI CTCAE) version 4. Adverse events not specifically defined in the NCI CTCAE will be scored on the Adverse Event log according to the general guidelines provided by the NCI CTCAE and as outlined below.

- Grade 1: Mild
- Grade 2: Moderate
- Grade 3: Severe or medically significant but not immediately life threatening
- Grade 4: Life threatening consequences
- Grade 5: Death related to the adverse event

10.2.3 Serious Adverse Events

ICH Guideline E2A and the UTSW IRB define serious adverse events as those events, occurring at any dose, which meets any of the following criteria:

- Results in death
- Immediately life-threatening
- Results in inpatient hospitalization or prolongation of existing hospitalization
- Results in persistent or significant disability/incapacity
- Results in a congenital anomaly/birth defect
- Based upon appropriate medical judgment, may jeopardize the subject's health and may require medical or surgical intervention to prevent one of the other outcomes listed in this definition.

Note: A "Serious adverse event" is by definition an event that meets any of the above criteria. Serious adverse events may or may not be related to the research project. A serious adverse event determination does not require the event to be related to the research. That is, both events completely unrelated to the condition under study and events that are expected in the context of the condition under study may be serious adverse events, independent of relatedness to the study itself. As examples, a car accident requiring overnight hospitalization would be a serious adverse event for any research participant; likewise, in a study investigating end-stage cancer care, any hospitalization or death would be a serious adverse event, even if the event observed is a primary clinical endpoint of the study. Refer to the UTSW IRB website at <http://www.utsouthwestern.net/intranet/research/research-administration/irb/study-management/adverse-events.html> to determine when a serious adverse event requires reporting to the IRB.

10.2.4 Unanticipated Problems:

The term "unanticipated problem" is found, but not defined in the regulations for the Protection of Human Subjects at 45 CFR 46, and the FDA regulations at 21 CFR 56. Guidance from the regulatory agencies considers unanticipated problems to include any incident, experience, or outcome that meets each of the following criteria:

- Unexpected (in terms of nature, severity or frequency) AND
- Definitely, probably, or possibly related to participation in the research AND
- Serious or a possible unexpected problem in that the research places subjects or others at greater risk of harm than was previously known or recognized. Note: Any serious adverse event would always suggest a greater risk of harm.

10.2.5 Follow-up

All adverse events will be followed up according to good medical practices.

10.2.6 Reporting

Local unanticipated problems require expedited reporting, and are submitted to the UTSW IRB through the UTSW eIRB and to the SCC DSMC Coordinator. Hardcopies or electronic versions of the eIRB report; FDA Form #3500A forms, or other sponsor forms, if applicable; and/or any other supporting documentation available should be forwarded to the DSMC Coordinator. The DSMC Coordinator forwards the information onto the DSMC Chairman who determines if immediate action is required. Follow-up eIRB reports, and all subsequent SAE

documentation that is available are also submitted to the DSMC Chair who determines if further action is required.

All local serious adverse events which occur on research subjects on protocols for which the SCC is the DSMC of record require reporting to the DSMC regardless of whether IRB reporting is required. Hardcopies or electronic versions of the FDA Form #3500A forms, or other sponsor forms, if applicable; and/or any other supporting documentation available should be forwarded to the DSMC Coordinator.

If the event occurs on a multi-institutional clinical trial coordinated by the Cancer Center, the DOT Manager or lead coordinator ensures that all participating sites are notified of the event and resulting action, according to FDA guidance for expedited reporting. DSMC Chairperson reviews all serious adverse events within upon receipt from the DSMC Coordinator. The DSMC Chairperson determines whether action is required and either takes action immediately, convenes a special DSMC session (physical or electronic), or defers the action until a regularly scheduled DSMC meeting.

Participating sites of multi-institutional clinical trials coordinated by the UTSW Radiation Oncology:

Written reports to:

UTSW Radiation Oncology Study Coordinator or Clinical Research Manager within 1 working day to

Study Coordinator: [name] at [contact] or

Clinical Research Manager: [name] at [contact]

[contact]

UTSW Radiation Oncology Study Coordinator or Clinical Research Manager will report to UTSW SCC Data Safety Monitoring Committee Coordinator

UTSW SCC Data Safety Monitoring Committee Coordinator

Email: [contact]

[contact] or deliver to NB 2.418

UTSW Institutional Review Board (IRB)

Submit via eIRB with a copy of the final sponsor report as attached supporting documentation

1. SAEs

Local serious adverse events (SAEs) for studies where SCC DSMC is the DSMC of record require reporting to the DSMC coordinator within 2 working days of PI awareness, or as described in the protocol.

2. Unanticipated Problems

- Local unanticipated problems require reporting to the UTSW IRB within 2 working days of PI awareness of the event.
- Unanticipated problems, including those that occur as non-local events, require reporting to the UTSW IRB within 10 working days of PI awareness of the event.

For further guidance for Investigators regarding safety reporting requirements for INDs and BA/BE studies, refer to FDA Draft Guidance document:

<http://www.fda.gov/downloads/Drugs/GuidanceComplianceRegulatoryInformation/Guidances/UCM227351.pdf>

